### Sample size calculations overview

	Protocol	Randomisation
Minimum Detectable Effect Size (MDES)	0.3	0.3
Alpha	0.05	0.05
Power	0.8	0.8

		Protocol	Randomisation
One-sided or two-sided?		Two-sided	Two-sided
Number of participants	intervention	176	176
	control	176	176
	total	352	352

The planned number of the trial participants is 352 CYP in its one year of implementation, 176 in the RM group and 176 in the RC group. The sample size is such that the trial is sufficiently powered to detect a Cohen’s d of at least 0.3 with probability 80%, which is in line with the funder guidelines and the previous literature.

The “simple” randomisation method will be used, which is a robust method against selection and accidental biases. We will use the statistical software package Matlab to implement the randomisation. Automated randomisation will ensure that the process is transparent and reproducible.

The above rest on the assumption that the alpha is equal to 0.05 and that the power is equal to 0.8. The minimum detectable effect size is equal to 0.3 as measured by Cohen’s d.

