### Primary outcome analysis

The aim of the analysis is to answer the research question: did the Restorative Mentoring intervention (treatment) reduce post-treatment contact with the police compared to the Restorative Choices intervention (control)?

The primary outcome for this study is contact with the police, defined as the number of times the CYP appear in the police data as perpetrators, victims or for missing person episodes. These data will be taken from Greater Manchester Police administrative records.

Contact with the police is a discrete count variable starting at 0. These data will be collected one month before the trial ends, for a period 1 year prior to the recruitment date and for 3 months after completion of the intervention for all CYP.

It should be noted that the primary outcome, which is police contact with the CYP, is susceptible to biases in reporting and recording of crimes. These biases may stem from a number of factors, including characteristics of both the victim and the offender, such as ethnicity and gender. Nevertheless, we anticipate that the RCT design remains robust to these biases, as randomisation into the treatment and control groups is conducted independently of the police's reporting and recording of crimes.

There are two ways of analysing the data, depending on the distribution assumed for the dependent variable, which is total police contacts. As a discrete count random variable, it may be assumed to follow a Poisson or Negative Binomial distribution. However, if the mean of that distribution is far from 0, the Poisson and Negative Binomial distributions may be approximated by the continuous normal distribution. It is not clear a priori which distribution will be the better approximation, and therefore we consider below both scenarios. In any case, we do not expect major differences; the issue of whether a variable should be treated as continuous or discrete has received much attention in the randomized control trial literature and the main finding is that unless the outcome is binary or it is a "time to a first event", information will not be lost when treating a count variable as a continuous one, see, e.g. Herbison et al. (2015).

For the analysis, the headline estimate will be derived from an intention to treat effect (ITT), denoted by  $\beta$  in the regression:

$$g[E(Y_i|T_i)] = \alpha + \beta T_i,$$

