where  $Y_i$  is the primary outcome for individual  $i$ , and  $T_i$  is an indicator variable equal to 1 if person  $i$  was assigned to treatment and 0 if person  $i$  was assigned to the control group. The function  $g$  is the link function and is equal to the natural logarithm function if the dependent variable is assumed to be Poisson or Negative Binomial.

Hypothesis testing in the above regression complies with the power predictions of the study. The effect size will be measured by the Incidence Rate Ratio if the data are assumed to be Poisson or Negative Binomial, and by Cohen's  $d$  if they are assumed approximately normal. If the data are Poisson/Negative Binomially distributed, the necessary sample size to detect a "small" effect of at least 1.22, see e.g. Cohen (1992) and Olivier et al. (2017), with  $\alpha=0.05$  and

80% power is 322 CYP equally split between the treatment and control groups. Alternatively, if the data are assumed to be normally distributed, then to detect a “small” effect size of at least 0.3 is 352 CYP. Therefore, a sample of 352 CYP will lead to as sufficiently powered study irrespective of the data distributional assumption.

We will additionally estimate a regression with covariates:

$$g[E(Y_i|T_i, Z_i)] = \alpha + \beta T_i + Z_i' \gamma,$$

where  $Z_i$  is a vector of individual characteristics that are not affected by the intervention (sex, age, ethnicity, district, the number of contacts with the police in the year prior to referral, and referral source). The analysis below depends on the over-arching assumption that the sample of observations are independent to each other. This is reasonable as the sample is only a small subset of the whole population.

The dependent variable here is a count variable and it is highly likely that the lower values will have much higher frequency, in other words it is heavily skewed to the right. This feature of the data suggests that they are best analysed using Poisson regression. Mathematically, the Poisson regression takes the form:

$$Y_i | \lambda_i \sim Poi(\lambda_i)$$

where  $\lambda_i = \alpha + \beta T_i + Z_i' \gamma$ .

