An additional assumption that needs to hold for the Poisson regression is that conditionally on the regressors, the mean and variance of  $Y_i$  must be equal to each other. This is called equidispersion. If this assumption does not hold and the variance is greater than the mean, then we must estimate the model using the Negative Binomial regression, which is able to deal with what is called overdispersion.

The Negative Binomial regression works for the same type of data as the Poisson regression, however it also contains an additional term which captures the excess variance, as typically the variance is greater than the mean, when they are not equal. The Negative Binomial distribution is a Poisson-gamma mixture, where a gamma noise variable which has a mean of 1 and a scale parameter of  $\nu$  has been included resulting in the following distribution:

---

 This calculation is based on the average number of police contacts for the control group in the pilot study, which is 1.8. Given that the pilot study participants did not have a full six-month follow-up it is expected that in the efficacy study this average will be much higher. However, the higher the average, the fewer observations are necessary for the power calculations. Therefore, 322 observations is a conservative estimate given that even fewer may be required.

$$P(Y = y_i | \mu_i, a) = \frac{\Gamma(y_i + a^{-1})}{\Gamma(y_i + 1)\Gamma(a^{-1})} \left( \frac{a^{-1}}{a^{-1} + \mu_i} \right)^{a^{-1}} \left( \frac{\mu_i}{a^{-1} + \mu_i} \right)^{y_i}$$

Where  $\mu_i = t_i\mu$  and  $a = 1/v$ . The parameter  $\mu$  may be interpreted as the risk of a new occurrence of the event during a specified exposure period  $t$ .

If the dependent variable can be approximated by the continuous normal distribution, then the regression models above become linear and will be estimated by least squares. In this case, the coefficient  $\beta$  is numerically equal to the difference of means between the control and the treatment group.

Finally, as it is expected that compliance will not be perfect, the analysis will involve estimating a local average treatment effect (LATE), which will provide an estimate of the treatment effect for individuals who engage with the intervention ([Imbens & Angrist \(1994\)](#), [Imbens & Wooldridge \(2009\)](#)). In this case, treatment assignment will be used as an instrument for whether individuals get treated or not (see Compliance section).

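### The count-model sample size of 322 does not follow from the SAP's printed inputs: the effect size of 1.22 and the N are inconsistent, and the documents do not show which is wrong

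*SAP*

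**What the plan says.** The SAP's section Sample size calculations overview tabulates alpha 0.05, power 0.8 and a two-sided test, and adds: "The above rest on the assumption that the alpha is equal to 0.05 and that the power is equal to 0.8". The target there is a Cohen's d of 0.3, with 176 CYP per arm.

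The section Primary outcome analysis adds a second calculation for the count models. It sets the scale: "The effect size will be measured by the Incidence Rate Ratio if the data are assumed to be Poisson or Negative Binomial". The target is an "effect of at least 1.22", and the number needed with alpha 0.05 and "80% power is 322 CYP equally split between the treatment and control groups". Sidedness is not restated there. Footnote 2 supplies the remaining input: "This calculation is based on the average number of police contacts for the control group in the pilot study, which is 1.8". The same footnote calls 322 conservative, because the pilot lacked a full six-month follow-up and a higher mean is therefore expected.

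The section concludes that 352 CYP give enough power whichever distribution is assumed. It gives no formula, no direction for the ratio and no dispersion value. The treatment indicator equals 1 for RM, and the research question is whether RM lowers police contact relative to RC.

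**The concern.** Three things look wrong before any formula is chosen.

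- **Direction.** With RM coded 1, an IRR of 1.22 means that RM raises police contacts by 22%. The trial is looking for a reduction.
- **Order of the two sample sizes.** At a Poisson mean of 1.8, a ratio of 1.22 is a standardised difference of about 0.28, and its inverse is about 0.25. Both are smaller than 0.3, for which the same section requires 352. A smaller effect cannot need fewer participants, yet the SAP gives 322.
- **Scope.** One N is offered for Poisson and Negative Binomial data alike, although the second has the larger variance.

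This is the only power statement for the count models on the primary outcome. If it stands uncorrected, a null result from a Poisson or Negative Binomial analysis would be read as coming from a trial with at least 80% power for the stated effect, which the stated inputs do not support.

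**Working it through.** **Inputs, all from the SAP.** Two-sided alpha 0.05 and power 0.8 (Sample size calculations overview); ratio 1.22 on the IRR scale and equal allocation (Primary outcome analysis); control mean 1.8 (footnote 2). Hence z = 1.960 and 0.842, and (1.960 + 0.842)² = 7.849.

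**Formula (Poisson, Wald test on the log rate ratio).**

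n per arm = 7.849 × (1/m0 + 1/m1) / (ln IRR)², with m0 = 1.8 and m1 = 1.8 × IRR.

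**Attempt to reproduce 322 from the printed inputs.**

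- IRR 1.22: m1 = 2.196; 7.849 × (0.5556 + 0.4554) / 0.03954 = 200.7, so 201 per arm, **402** in total.
- IRR 1/1.22 = 0.82: m1 = 1.475; 7.849 × (0.5556 + 0.6778) / 0.03954 = 244.8, so 245 per arm, **490** in total.

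These exceed 322 by 25% (402/322) and 52% (490/322). Other two-sided versions were tried with the ratio 1.22 or its inverse: rate difference, pooled or control-rate null variance, square-root transformation, control variance only, 1.8 as the overall mean, and event-count formulas. All fall between 362 and 538. None gives 322.

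**Changes of input that do recover it.**

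- Two-sided, 22% reduction (IRR 0.78, m1 = 1.404). Rate-difference scale: 7.849 × (1.8 + 1.404) / 0.396² = 160.4, so 161 per arm, **322**. Log scale: 161.2, so 162 per arm, **324**.
- One-sided 5%, IRR 1.22, with (1.645 + 0.842)² = 6.183. Rate-difference scale: 157.5 per arm, **316**. Log scale: 158.1 per arm, **318**.

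**Power under Poisson variance, mean 1.8, two-sided.** Power = Φ(|ln IRR| / SE − 1.960), with SE = √[(1/m0 + 1/m1)/n].

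| Target IRR | SE, 176 per arm | Power, 352 CYP | Power, 322 CYP |
|---|---|---|---|
| 1.22 | 0.0758 | 74.7% | 70.9% |
| 0.82 | 0.0837 | 66.1% | 62.3% |
| 0.78 | 0.0849 | 83.3% | 80.0% |

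Simulation agreed for 352 CYP: 74.8% for IRR 1.22 and 66.3% for 0.82. With 352, the reduction detectable at 80% power is IRR 0.79.

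**Standardised differences**, using the average of the two Poisson variances: 0.396/√1.998 = 0.28 for IRR 1.22; 0.325/√1.638 = 0.25 for 0.82; 0.396/√1.602 = 0.31 for 0.78.

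**Overdispersion.** The documents give no dispersion value, so a range is assumed. A Negative Binomial dispersion a adds 2a to (1/m0 + 1/m1).

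| Assumed a | Power at 352, IRR 1.22 | IRR 0.82 | IRR 0.78 |
|---|---|---|---|
| 0.25 | 57% | 52% | 70% |
| 0.5 | 46% | 42% | 59% |
| 1 | 33% | 31% | 45% |

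**Control mean needed for 80% power with 352 (Poisson).** 7.849 × (1 + 1/IRR) / (ln IRR)² / 176 gives 2.05 for IRR 1.22 and 2.50 for 0.82.

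**The normal-theory figure.** For d = 0.3, 2 × 7.849 / 0.09 = 174.4, so 175 per arm; 176 per arm give 80.4%. That calculation is sound.

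**The case against.** The strongest reply is that 322 may be a correct number with the wrong label. A two-sided test of a 22% reduction gives exactly 322 on the rate-difference scale. It runs in the direction of the research question and respects the two-sided table. At IRR 0.78 the standardised difference is 0.31, above 0.3, so needing fewer than 352 is then what one would expect. This stands. The comparison with d = 0.3 proves that effect and N disagree, but cannot show which of them is at fault.

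A reader might therefore infer too much: that the trial has only 66% to 75% power, or that 322 must have come from a one-sided test. The documents support neither. The power range holds only if the target is 1.22 or its inverse, and without a formula the route to 322 cannot be established.

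Two further replies carry some weight. Footnote 2 expects a mean above 1.8, which would raise power. But it argues from a six-month follow-up, while the primary outcome covers 3 months after completion, and the SAP does not name the mean that would be needed. Secondly, the protocol justifies 352 by d = 0.3 alone, so the count calculation is supplementary. The SAP also says both that the better distribution is not known in advance and that skewed counts point to Poisson regression. The supplementary figure nevertheless carries the conclusion that power is adequate under either distribution.

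**Conclusion.** The concern holds as an inconsistency between the stated effect size and the stated N. From the printed inputs the Poisson requirement is 402 (IRR 1.22) or 490 (IRR 0.82), not 322, and 352 CYP give about 75% or 66% power. If the intended target was IRR 0.78, the N is about right, power at 352 is about 83%, and the error is the figure 1.22. The documents do not settle which. On either reading, 1.22 with RM coded 1 describes an increase in contacts.

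All these figures assume Poisson variance and a control mean of 1.8. Overdispersion lowers them and a higher mean raises them. With no dispersion value given, neither 322 for Negative Binomial data nor the adequacy of 352 under any distribution is supported. The finding does not show that 352 is too few for the trial's declared target of d = 0.3, which is correctly calculated.

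**What to change.** In the SAP's Primary outcome analysis and footnote 2, state the formula, keep the two-sided test, and give the target as an IRR below 1. Then correct the element that is wrong:

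- If the target is 0.82, the inverse of 1.22, replace 322 with 490, and state about 66% power at 352, with IRR 0.79 detectable at 80% power.
- If the target was a 22% reduction, replace 1.22 with 0.78, keep 322 to 324 according to the formula, and state about 83% power at 352.

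In either case:

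- Label the figures as Poisson at mean 1.8.
- Withdraw the claims that 322 covers Negative Binomial data and that 352 suffice whatever the distribution, or support them with a stated dispersion value.
- Remove the description of 322 as conservative, and reconcile footnote 2's six-month follow-up with the 3-month window of the primary outcome.

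The cost is SAP wording only. No extra enrolment is asked for, and the d = 0.3 calculation stays as it is. Under the 0.82 reading the reported power becomes less favourable.

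### The SAP's 322 CYP for a rate ratio of 1.22 does not follow from its own inputs, so 352 CYP are not enough under every distribution on the rate-ratio route

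*SAP*

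**What the plan says.** In the SAP's Primary outcome analysis, the effect measure is the incidence rate ratio if the counts are treated as Poisson or Negative Binomial, and Cohen's d if they are treated as approximately normal. For the count route it takes a small "effect of at least 1.22" and says that the number needed at "80% power is 322 CYP equally split between the treatment and control groups". For the normal route it gives 352 CYP for d = 0.3. It then concludes: "Therefore, a sample of 352 CYP will lead to as sufficiently powered study irrespective of the data distributional assumption".

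Footnote 2 supplies the only other input: "This calculation is based on the average number of police contacts for the control group in the pilot study, which is 1.8". It calls 322 conservative because pilot participants "did not have a full six-month follow-up it is expected that in the efficacy study this average will be much higher", and a higher mean needs fewer observations.

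The SAP's sample size section states: "The above rest on the assumption that the alpha is equal to 0.05 and that the power is equal to 0.8". Its table, like Table 3 of the protocol, specifies a two-sided test. The research question in the primary outcome section is whether restorative mentoring lowers police contact relative to the control. The same section plans Poisson regression, with Negative Binomial regression if the variance exceeds the mean. It remarks that "typically the variance is greater than the mean" in cases where the two differ. Neither document gives a dispersion value.

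**The concern.** Three parts of the power statement do not fit together. The 322 looks too small for its stated inputs. One sample size is offered for two models, although the Negative Binomial number depends on a dispersion value that is not given. And the claim that 322 is conservative rests on a rise in the mean, which is argued from a follow-up length that does not obviously match the outcome window.

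This is the power statement for the primary outcome, and the SAP says that a right-skewed count is best analysed by Poisson regression. The count route is thus the one likely to be used. If its power is overstated, a null rate ratio could be given more weight as evidence against a small effect than the trial can support.

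**Working it through.** **Inputs.** Control mean m0 = 1.8 (SAP footnote 2); ratio 1.22 and 80% power (SAP, Primary outcome analysis); two-sided alpha 0.05 (SAP and protocol sample size tables); 1:1 allocation, 352 CYP, so 176 per arm. Dispersion k is not in the documents; the values below are assumptions shown as a range. k = 0 is Poisson.

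**Formula.** Wald test on the log rate ratio:

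n per arm = (1.960 + 0.842)² × (1/m0 + 1/m1 + 2k) / (ln RR)², where (1.960 + 0.842)² = 7.849 and (ln 1.22)² = 0.03954.

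**Trying to reproduce 322, Poisson, two-sided**

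- RR = 1.22: m1 = 2.196; 1/1.8 + 1/2.196 = 1.0109; n = 7.849 × 1.0109 / 0.03954 = 200.7, so 201 per arm, 402 in total.
- RR = 1/1.22 = 0.82: m1 = 1.475; 1/1.8 + 1/1.475 = 1.2333; n = 7.849 × 1.2333 / 0.03954 = 244.8, so 245 per arm, 490 in total.

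The rate-difference formula, n = 7.849 × (m0 + m1)/(m0 − m1)², gives the same totals (200.006 and 244.007 per arm before rounding up). Other two-sided variants (square-root transform, null-pooled variance, conditional binomial, event-count formulas and others) gave 362 to 446 for 1.22 and 442 to 538 for 1/1.22. None gave 322.

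Two calculations come close to 322:

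- A ratio of 0.78 (1.8 to 1.404) by the rate-difference formula: 7.849 × 3.204 / 0.396² = 160.4, so 161 per arm, 322 in total. On the SAP's log link the same ratio gives 161.2 per arm, or 324.
- A one-sided 5% test of an increase to 1.22: 318 by the Wald formula. One-sided for 1/1.22 needs 386.

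The first uses a larger effect than the one stated. The second contradicts the two-sided design and points away from the research question. Which of them, if either, was used is unknown.

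**Power of 352 CYP**, from SE² = (1/m0 + 1/m1 + 2k)/176 and power = Φ(0.1989/SE − 1.960):

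| k | Power, 1.22 | Power, 1/1.22 | CYP for 80%, 1.22 | CYP for 80%, 1/1.22 |
|---|---|---|---|---|
| 0 (Poisson) | 74.7% | 66.1% | 402 | 490 |
| 0.1 | 67% | 60% | 482 | 570 |
| 0.25 | 57% | 52% | 600 | 690 |
| 0.5 | 46% | 42% | 800 | 888 |
| 1 | 33% | 31% | 1,196 | 1,284 |

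Simulation of the Poisson case (400,000 runs) gave 74.8% and 66.2%.

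**Would a higher mean rescue it?** Set n = 176 and solve for m0. Under Poisson, 1.22 needs m0 = 7.849 × (1 + 1/1.22)/(176 × 0.03954) = 2.05. For 1/1.22, m0 = 7.849 × 2.22/(176 × 0.03954) = 2.50. As the mean grows, only the term 2k remains, so 80% power at any mean requires k below 176 × 0.03954/(2 × 7.849) = 0.44.

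**Reduction detectable with 352 CYP at mean 1.8** (same formula solved for RR, 80% power): about 0.79 for Poisson, 0.72 at k = 0.5, 0.68 at k = 1 and 0.61 at k = 2.

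**The normal route.** For d = 0.3 the normal approximation gives 2 × 7.849/0.09 = 174.4, so 175 per arm, 350 in total. The t-test gives 176 per arm, 352 in total, with 80.1% power. This figure reproduces. Its meaning in counts depends on dispersion, because the count variance is m + km²:

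- k = 0: means 1.8 and 1.42; pooled SD = √((1.8 + 1.42)/2) = 1.27; difference 0.38; d = 0.30. That is about a 21% reduction.
- k = 1: means 1.8 and 1.21; variances 5.04 and 2.68; pooled SD = √3.86 = 1.96; difference 0.59; d = 0.30. That is about a 33% reduction.

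**The case against.** The best reply is that the design effect size in both documents is d = 0.3, and 352 is right for it. That stands. A reader might infer that the trial has no valid 80% power statement for its primary outcome; the documents do not support this. Because d is scaled by the SD, overdispersion is already in its denominator. What fails is the 1.22 figure and the extension of sufficiency to every distribution.

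A second reply is that the mean will be higher than 1.8. Under pure Poisson a mean of about 2.05 (or 2.5 for the reduction) would indeed be enough. But the SAP gives no value for the higher mean, and the argument does not remove the dispersion term.

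Footnote 2's six months may also be read as a flat contradiction of the three-month window. That is too strong. Restorative mentoring lasts 12 weeks and counting ends 3 months after completion, so six months could run from the start of mentoring. The outcome definition favours 3 months after completion, so the window needs clarifying. Nor should the mean simply be halved to 0.9: the pilot had less than a full six months, so proportional scaling to three months leaves more than 0.9.

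Finally, the SAP does not forecast overdispersion outright. Its remark on the variance is conditional, and Negative Binomial regression is the fallback. The Poisson shortfall needs no such forecast.

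**Conclusion.** The concern holds for the rate-ratio route. With the SAP's own inputs, 322 should be 402 for a ratio of 1.22 or 490 for the matching reduction. Both exceed 352, so the all-distributions claim fails even with no overdispersion, and with only the documents' figures. The further loss of power under Negative Binomial data rests on assumed dispersion and is a range, not an estimate for this trial. The description of 322 as conservative is unsupported. The 352 for d = 0.3 stands, provided that its meaning as a percentage reduction is understood to vary with dispersion.

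**What to change.** In the SAP, delete the 322 figure, the sentence that 352 is enough under any distribution, and footnote 2's claim that 322 is conservative. Replace them with the minimum detectable rate ratio for 352 CYP, expressed as a reduction, at two-sided alpha 0.05 and 80% power. Compute it under a Negative Binomial model from the pilot control-group mean and variance, scaled to the actual outcome window, and show a short table over dispersion. State the pilot's follow-up length and whether the window runs from completion or from the start of the intervention. Keep the d = 0.3 statement and the target of 352.

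The cost is one calculation, assuming that the evaluator still holds the pilot counts, and a few lines of text. Recruitment, data collection, model and test are unchanged. The stated power becomes less favourable.

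### The SAP's claim that 352 CYP suffice whatever the count distribution is unsupported: the 322 figure leaves no room for overdispersion and is not reproduced with two-sided alpha

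*SAP*

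**What the plan says.** The SAP, Primary outcome analysis, covers both count models with a single calculation. For a rate ratio of at least 1.22 with alpha 0.05, the sample needed for "80% power is 322 CYP equally split between the treatment and control groups". For normally distributed data it gives 352 for a Cohen's d of 0.3. It then concludes: "Therefore, a sample of 352 CYP will lead to as sufficiently powered study irrespective of the data distributional assumption".

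Footnote 2 gives the only other input to the count calculation: "This calculation is based on the average number of police contacts for the control group in the pilot study, which is 1.8". It argues that participants in the pilot lacked a full six-month follow-up, so "it is expected that in the efficacy study this average will be much higher", and adds: "However, the higher the average, the fewer observations are necessary for the power calculations". On that ground it calls 322 conservative.

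The same section treats Poisson regression as the natural first choice for these skewed counts. It makes Negative Binomial regression obligatory if the variance exceeds the mean. It describes the Negative Binomial's extra term as capturing excess variance, "as typically the variance is greater than the mean, when they are not equal", and writes the distribution with a separate dispersion parameter, a.

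The Sample size calculations overview specifies a two-sided test and says: "The above rest on the assumption that the alpha is equal to 0.05 and that the power is equal to 0.8". The research question asks whether RM reduces police contact compared with RC.

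**The concern.** Sample size for Negative Binomial counts depends on the dispersion as well as the mean, because the variance is mean + a × mean². Neither document states a dispersion, variance or standard deviation for police contacts. One figure can serve both count models only if a is close to zero, and in that case the Negative Binomial has not been allowed for. Footnote 2's reasoning, that a higher mean always lowers the requirement, holds without limit only for Poisson counts.

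This is the power statement for the primary outcome, and the SAP says its hypothesis testing conforms to it. If power is well below 80%, an inconclusive primary result says less about absence of benefit than the SAP would lead a reader to think.

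**Working it through.** **Inputs.** Control mean m0 = 1.8 (SAP footnote 2). Rate ratio 1.22, 80% power and alpha 0.05 (SAP, Primary outcome analysis). Two-sided test and 176 per arm (SAP, Sample size calculations overview). Dispersion a: not given, so a range is assumed.

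**Formula.** Wald test on the log rate ratio:

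n per arm = (z_alpha + z_power)² × (1/m0 + 1/m1 + 2a) / ln(IRR)²

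Here ln(1.22)² = 0.03954. For an increase m1 = 1.8 × 1.22 = 2.196, so 1/m0 + 1/m1 = 0.5556 + 0.4554 = 1.0109. For a decrease m1 = 1.8/1.22 = 1.475, and the sum is 0.5556 + 0.6778 = 1.2333.

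**Step 1: reproduce 322, with a = 0.**
- One-sided, increase: (1.645 + 0.842)² = 6.183; 6.183 × 1.0109 / 0.03954 = 158.1 per arm, total 316 to 318.
- Two-sided, increase: (1.960 + 0.842)² = 7.849; 7.849 × 1.0109 / 0.03954 = 200.7 per arm, total 402.
- Two-sided, decrease: 7.849 × 1.2333 / 0.03954 = 244.8 per arm, total 490.

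Other two-sided Poisson methods for an increase (rate difference, square root, conditional binomial, Signorini) give 399 to 429. A rate difference with both variances set at 1.8 gives 360. None gives 322. Solving the formula for a at 161 per arm gives 0.009 one-sided and −0.10 two-sided, so 322 contains no meaningful overdispersion.

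The normal-model figure does reproduce: d = 0.3 needs 350 in total, and 176 per arm gives 80.4% power.

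**Step 2: two-sided power at 176 per arm.** Power = Φ(ln(1.22) / √[(1/m0 + 1/m1 + 2a)/176] − 1.960). For example, at a = 0.25 and mean 1.8: √[(1.0109 + 0.5)/176] = 0.0927; 0.1989/0.0927 − 1.960 = 0.186; Φ = 57%. The decrease to 1/1.22 is in brackets.

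| a (assumed) | Mean 1.8 | Mean 3.6 | Total n for 80% at mean 1.8 |
|---|---|---|---|
| 0 (Poisson) | 75% (66%) | 96% (92%) | 402 (490) |
| 0.1 | 67% (60%) | 88% (83%) | 482 (570) |
| 0.25 | 57% (52%) | 75% (70%) | 600 (690) |
| 0.5 | 46% (42%) | 58% (55%) | 800 (888) |
| 1 | 33% (31%) | 39% (37%) | 1196 (1284) |

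The mean of 3.6 is simply double the pilot value, because the SAP does not say how much higher it expects the mean to be.

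Simulated Negative Binomial regression at mean 1.8 (600 runs per cell) gave 59%, 48% and 38% for an increase at a = 0.25, 0.5 and 1, and 54%, 46% and 32% for a decrease. All are within about 5 points of the formula.

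**Step 3: test footnote 2's argument.** As the mean grows, 1/m0 + 1/m1 tends to zero but 2a stays. With 176 per arm, 80% power is out of reach at any mean if a > 176 × 0.03954 / (2 × 7.849) = 0.44. With 161 per arm the limit is 0.41. However large the mean, power at 352 tends to only about 75% at a = 0.5 and 46% at a = 1.

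**Step 4: detectable reduction.** With 352, 80% power and mean 1.8, the detectable rate ratio is about 0.79, 0.75, 0.72 and 0.68 for a = 0, 0.25, 0.5 and 1. The reference value is 1/1.22 = 0.82.

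**The case against.** The best defence is that the SAP names Poisson first, keeps Negative Binomial as a fallback, and expects a mean well above 1.8. Part of that stands. Under Poisson, 352 reaches 80% two-sided once the control mean is about 2.05 (2.50 for a decrease). With a = 0.1 and a mean of 3.6, power is 88% (83%). So the sample may prove adequate if dispersion is low and the mean rises.

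That is a conditional case, and the SAP's sentence is unconditional. The expected rise is also uncertain: footnote 2 argues from a six-month follow-up, while the outcome window in the same section is 3 months after completion.

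A reader might go further than the documents allow in four ways.
- **That power is a specific low figure, such as 33% to 57%.** Those values come from assumed a of 0.25 to 1 at mean 1.8. The documents give no dispersion.
- **That the SAP expects to use Negative Binomial.** Its remark on variance gives the usual direction of any departure from equality, not a forecast. Right skew is no proof of overdispersion either, since a Poisson variable with mean 1.8 is itself right-skewed.
- **That overdispersion explains the whole shortfall.** At mean 1.8, power is already about 75% (66%) with none.
- **That the SAP's authors used a one-sided test.** The one-sided match is close but not exact, and the SAP does not name its formula. What can be said is that 322 is not reproduced with the stated two-sided alpha.

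**Conclusion.** The claim of sufficient power under any distribution is unsupported. At the SAP's own mean of 1.8, two-sided power at 352 for a rate ratio of 1.22 is below 80% under every count model: about 75% for Poisson (66% for a decrease), and lower with any overdispersion. Footnote 2's case that 322 is conservative fails as a general argument, because a higher mean does not shrink the dispersion term.

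These results rest on the Wald log-rate formula, 1:1 allocation and the pilot mean. The Negative Binomial percentages also rest on assumed dispersions. The documents do not show that the trial is underpowered at the mean and dispersion it will actually observe. The normal-model calculation for d = 0.3 is not in question.

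**What to change.** In the SAP, Primary outcome analysis:
1. Delete the closing claim that power is adequate regardless of distribution, and footnote 2's argument that 322 is conservative.
2. Recompute the 322 figure with two-sided alpha for a reduction in contacts, and name the formula.
3. Estimate the dispersion from the pilot police counts if they are available (the documents report only their mean); otherwise use a stated range.
4. Report power and the detectable rate ratio for the planned 352 in a small table, over dispersion 0 to 1 and at least two control means. State the follow-up window to which each mean refers.

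The cost is one calculation and a rewritten paragraph. No extra enrolment or design change is needed. The downside is a less favourable stated power.
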